## 11.6. Electrocardiogram (ECG)

The following ECG data will be collected: heart rate, PR interval, QRS width, QT interval and Bazett's and Fridericia QTc interval (QTcB and QTcF).

The change from baseline will be calculated and summary statistics will be tabulated for both absolute values and change from baseline by treatment group, visit and dose level. Abnormal findings will be tabulated by visit showing a frequency count and percentage of subjects with at least one abnormal finding.

ECG results will be listed and abnormal findings will be marked, together with an indication of whether or not that finding was clinically significant. Values with a change from baseline > 30 msec in QT interval, QTcB and QTcF will be flagged in the listing.

The following reference ranges will be used to determine the categories for the ECG shift table, and to mark the abnormal (high/low) findings in the ECG listing:

- Heart rate: Low < 40 msec; Normal  $\geq$  40 msec to  $\leq$  110 msec; High > 110 msec
- PR interval: Low < 120 msec; Normal  $\geq$  120 msec to  $\leq$  220 msec; High > 220 msec
- QRS width: Low < 70 msec; Normal  $\geq$  70 msec to  $\leq$  120 msec; High > 120 msec
- QT interval: Low < 330 msec; Normal  $\geq$  330 msec to  $\leq$  450 msec; High > 450 msec
- QTcB: Low < 350 msec; Normal  $\geq$  350 msec to  $\leq$  450 msec; High > 450 msec
- QTcF: Low < 350 msec; Normal  $\geq$  350 msec to  $\leq$  450 msec; High > 450 msec

## 11.7. Other safety evaluations

### 11.7.1. Physical examination

A shift table of baseline assessment of full physical examination to week 24/End of Study (EOS) by category, pre-baseline therapy and treatment group will be produced. At screening and week 24/EOS, if the eCRF confirms the physical examination has been performed and there are no abnormalities, a 'Normal' status will be imputed for each of the physical examination categories:

- General
- Cardiovascular
- Neurological
- Gastrointestinal
- Respiratory
- Skin
- Head, eyes, ears, nose & throat

- Musculoskeletal including extremities
- Genitourinary
- Other

Abnormal physical examination status categories are captured in the eCRF, together whether the finding was clinically significant.

Physical examination results will be listed and abnormal findings will be marked, together with an indication of whether or not that finding was clinically significant.

### 11.7.2. Concomitant medications excluding glucocorticoid steroids

Concomitant medications excluding glucocorticoid steroids[a], which include medications that began prior to date of randomisation but were ongoing after first dose of randomised treatment or started after the start of randomised treatment, will be summarised descriptively by ATC text, generic term, and treatment group using counts and percentages as appropriate.

A detailed listing of all concomitant medications excluding glucocorticoid steroids will be listed.

[a] The following list of steroids will be excluded from the summaries and listings of concomitant medications and instead will be reported under *sick day medications and steroids taken in addition to IMP* (see section 11.7.3).

ATCCODE	LEVEL	ATC Text
D07AC	4	Corticosteroids, potent (group III)
D07AD	4	Corticosteroids, very potent (group IV)
H02	2	CORTICOSTEROIDS FOR SYSTEMIC USE
H02A	3	CORTICOSTEROIDS FOR SYSTEMIC USE, PLAIN
H02AA	4	Mineralocorticoids
H02AB	4	Glucocorticoids [b]
H02B	3	CORTICOSTEROIDS FOR SYSTEMIC USE, COMBINATIONS
H02BX	4	Corticosteroids for systemic use, combinations
R01AD	4	Corticosteroids
R03BA	4	Glucocorticoids
S01BA	4	Corticosteroids, plain
S02B	3	CORTICOSTEROIDS
S02BA	4	Corticosteroids
S03B	3	CORTICOSTEROIDS
S03BA	4	Corticosteroids

[b] Excluding Fludrocortisone, which will be summarised alongside concomitant medication.

### 11.7.3. Use of dispensed sick day medications and steroids taken in addition to IMP

Use of dispensed sick day medications by route and drug name and steroids taken in addition to IMP (which includes medications that began prior to the date of randomisation but were ongoing after first dose of randomised treatment or started after randomised treatment) by ATC text and generic term will be summarised by treatment group.

A detailed listing of all dispensed sick day medications and steroids taken in addition to IMP will be produced.

#### 11.7.4. Adrenal insufficiency

Signs and symptoms of adrenal insufficiency will be summarised by treatment group and visit. A listing of all signs and symptoms of adrenal insufficiency will be produced flagging any significant findings and significant findings related to under/over replacement of steroid.

## 12. Changes from the planned analyses

At the time of finalising the SAP version 2.0, there are minor changes from the planned analyses specified in the protocol. For routine clinical laboratory variables (haematology and clinical biochemistry) shift tables to each visit relative to baseline have been replaced with shift tables to minimum on-treatment versus baseline and to maximum on-treatment versus baseline. This is judged to be a more conservative approach to detecting potential safety signals from clinical laboratory data. For vital signs, the split by dose level has been removed from the summaries of absolute values and change from baseline over time, due to the low number of subjects per category. Instead this will be assessed via listings. For a similar reason, the split by dose level has been removed from the summary of abnormal ECG results.

## 14. Appendix A – List of tables, listings and figures

### 14.1. List of planned tables

#### Study population

Subject disposition (All subjects)

Protocol deviations (All subjects)

Analysis sets (All subjects)

Demographic characteristics (Safety analysis set)

Baseline disease characteristics (Safety analysis set)

CAH medical history (Safety analysis set)

Other medical history excluding CAH events (Safety analysis set)

Prior medications (Safety analysis set)

Concomitant medications excluding steroids (Safety analysis set)

Use of sick day medication and steroids taken in addition to IMP (Safety analysis set)

Subject compliance (Safety analysis set)

Use of glucocorticoids: last dose prior to each visit (Safety analysis set)

Table of change from baseline to each visit in dose (hydrocortisone equivalent) of last glucocorticoid (Safety analysis set)

Categories of hydrocortisone dose equivalent increments versus baseline (Safety analysis set)

#### Safety

Duration of exposure (Safety analysis set)

Dose titrations recommended by the independent blinded physician (Safety analysis set)

Reasons for dose increases and reductions recommended by the independent blinded physician (Safety analysis set)

Table of dose titrations instructed by the Investigator (Safety analysis set)

Reasons for dose changes instructed by the Investigator (Safety analysis set)

Adverse event in any category - subject level (Safety analysis set)

Adverse event in any category - episode level (Safety analysis set)

Listing of deaths (Safety analysis set)

Adverse events leading to death (Safety analysis set)

Listing of adverse events leading to death (safety analysis set)

All adverse events (Safety analysis set)

All serious adverse events (Safety analysis set)

Listing of all serious adverse events (Safety analysis set)

Adverse events leading to discontinuation of study treatment (Safety analysis set)

Listing of adverse events leading to discontinuation of study treatment (Safety analysis set)

Adverse events by causality (Safety analysis set)

Adverse events by action taken (Safety analysis set)

Adverse events by outcome (Safety analysis set)

Adverse events by severity (Safety analysis set)

*Repeat above 6 tables for SAEs*

Most common (frequency of >10%) adverse events (Safety analysis set)

Most common (frequency of >1%) SAEs (Safety analysis set)

Adverse events leading to use of "sick day rules" (Safety analysis set)

Adverse events leading to use of “sick day rules” by sick day medication (Safety analysis set)

Adverse events leading to Adrenal crises (Safety analysis set)

Adverse events of unexpected therapeutic benefit (Safety analysis set)

*Repeat of AE Tables at episode level to be decided at Data Review meeting*

Signs and symptoms of adrenal insufficiency and over treatment (Safety analysis set)

Haematology (1) laboratory variables (Safety analysis set)

Change from baseline in Haematology (1) laboratory variables (Safety analysis set)

Shift table of baseline to minimum on-treatment for Haematology (1) laboratory variables (Safety analysis set)

Shift table of baseline to maximum on-treatment for Haematology (1) laboratory variables (Safety analysis set)

Haematology (1) results considered clinically significant by the investigator (Safety analysis set)

*Repeat above 5 tables for Haematology (2), Haematology (3)*

Biochemistry (1) laboratory variables (Safety analysis set)

Change from baseline in Biochemistry (1) laboratory variables (Safety analysis set)

Shift table of baseline to minimum on-treatment for Biochemistry (1) laboratory variables (Safety analysis set)

Shift table of baseline to maximum on-treatment for biochemistry (1) laboratory variables (Safety analysis set)

Biochemistry (1) results considered clinically significant by the investigator (Safety analysis set)

*Repeat above 5 tables for Biochemistry (2), Biochemistry (3), Biochemistry (4)*

Urinalysis results - continuous parameters (Safety analysis set)

Change from baseline for urinalysis results - continuous parameters (Safety analysis set)

Categorical urinalysis parameters (Safety analysis set)

Shift table of baseline to worst on-treatment for categorical urinalysis laboratory variables (Safety analysis set)

Continuous urinalysis parameters - results considered clinically significant by the investigator (Safety analysis set)

Categorical urinalysis parameters - results considered clinically significant by the investigator (Safety analysis set)

Vital signs variables (Safety analysis set)

Vital signs variables, change from baseline (Safety analysis set)

Vital signs shift table for SBP and DBP, baseline to minimum on-treatment (Safety analysis set)

Vital signs shift table for SBP and DBP, baseline to maximum on-treatment (Safety analysis set)

Electrocardiogram variables over time (Safety analysis set)

Electrocardiogram variables, change from baseline (Safety analysis set)

Abnormal electrocardiogram findings (Safety analysis set)

Physical examination - baseline versus end of study assessment (Safety analysis set)

## **Efficacy**

Primary efficacy analysis for 17-OHP, change from baseline to 24 weeks in primary efficacy variable, analysis of covariance model (Efficacy evaluable analysis set)

*Repeat above 1 table for weeks 4 and 12*

Secondary efficacy analysis of 17-OHP by pre-treatment strata, change from baseline to 24 weeks in primary efficacy variable, analysis of covariance model (Efficacy evaluable analysis set)

*Repeat above 1 table weeks 4 and 12*

Summary of absolute values of primary efficacy variable for 17-OHP, by visit (Efficacy evaluable analysis set)

Summary of change in baseline in primary efficacy variable for 17-OHP, by visit (Efficacy evaluable analysis set)

Secondary efficacy analysis of responders at 09:00h week 24 for 17-OHP, logistic regression model (Efficacy evaluable analysis set)

Summary of the 17-OHP results at 09:00h week 24 (Efficacy evaluable analysis set)

*Repeat all 17-OHP only Efficacy outputs above for the A4 hormone (including repeats)*

*Repeat all Efficacy outputs above in the Full analysis set (including repeats)*

Secondary efficacy analysis of change from baseline to 24 weeks in body composition - Dual Energy X-ray Absorptiometry, analysis of covariance model (Efficacy evaluable analysis set)

Summary of absolute values of body composition - Dual Energy X-ray Absorptiometry (Efficacy evaluable analysis set)

Summary of change from baseline in body composition - Dual Energy X-ray Absorptiometry (Efficacy evaluable analysis set)

Exploratory analysis of 17-OHP 8-hour profiles: change from baseline to 24 weeks in primary efficacy variable, analysis of covariance model (Efficacy evaluable analysis set)

*Above partial profile ANCOVA table to be repeated for separate pre-baseline strata*

*All partial profile outputs above to be repeated for A4 hormone (total of 2 tables)*

Summary of change from baseline for bone markers and laboratory assessments of special interest (Efficacy evaluable analysis set)

Summary of absolute values for bone markers and laboratory assessments of special interest (Efficacy evaluable analysis set)

Shift table of baseline to minimum on-treatment for bone markers and laboratory assessments of special interest (Efficacy evaluable analysis set)

Shift table of baseline to maximum on-treatment for bone markers and laboratory assessments of special interest (Efficacy evaluable analysis set)

Summary of clinically significant results for bone markers and laboratory assessments of special interest (Efficacy evaluable analysis set)

Summary of SF-36 scores (Efficacy evaluable analysis set)

Summary of SF-36 change from baseline (Efficacy evaluable analysis set)

Summary of SF-36 percentage change from baseline (Efficacy evaluable analysis set)

*Repeat above 3 tables for GFI, MAF and EQ-5D™*

## 14.2. List of planned listings

### Study population

Subject disposition (All subjects)

Protocol deviations (All subjects)

Listing of subjects with extreme visit deviations (All randomised subjects)

Subjects excluded from the safety analysis set

Subjects excluded from the full analysis set

Subjects excluded from the efficacy evaluable analysis set

Demographic characteristics (Safety analysis set)

Congenital adrenal hyperplasia medical history (Safety analysis set)

Mutation status

Other medical history excluding CAH related events (Safety analysis set)

Pre-baseline therapy strata (Safety analysis set)

Prior medications (Safety analysis set)

---

### Safety

Sick day pack accountability (Safety analysis set)

Steroids and other glucocorticoids taken in addition to IMP (Safety analysis set)

Sick day medication administration (Safety analysis set)

Treatment exposure (Safety analysis set)

Dose titrations recommended by the independent blinded physician (Safety analysis set)

Study drug accountability (Safety analysis set)

Unscheduled dose changes (Safety analysis set)

Investigator adherence to protocol defined dose titrations (Safety analysis set)

Dosing instructions provided to subjects from investigator (Safety analysis set)

Subject compliance (Safety analysis set)

All Adverse events (Safety analysis set)

Serious adverse events leading to death (Safety analysis set)

Adverse events leading to use of sick day rules (Safety analysis set)

Adverse events leading to adrenal crises (Safety analysis set)

Adverse events of unexpected therapeutic benefit (Safety analysis set)

Signs and symptoms of adrenal insufficiency and over treatment (Safety analysis set)

Haematology (1) laboratory variables (Safety analysis set)

*Repeat for Haematology (2), Haematology (3)*

Biochemistry (1) laboratory variables (Safety analysis set)

*Repeat for Biochemistry (2), Biochemistry (3), Biochemistry (4)*

Urinalysis laboratory variables (Safety analysis set)

Pregnancy test results (Safety analysis set)

Vital signs (Safety analysis set)

Electrocardiogram parameters (Safety analysis set)

Physical examination (Safety analysis set)

Concomitant medications excluding steroids (Safety analysis set)

---

### Efficacy

Bone markers and laboratory assessments of special interest (Efficacy evaluable analysis set)

DEXA scan parameters (Efficacy evaluable analysis set)

17-OHP and A4 (Full analysis set)

SF-36 scores (Efficacy evaluable analysis set)

MAF scores and GFI (Efficacy evaluable analysis set)

EQ-5D scores (Efficacy evaluable analysis set)

---

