Urine samples will be tested for the following;

- Pregnancy test in females of childbearing potential (this test will be done locally at the site)
- Protein, glucose, specific gravity, ketones, urobilinogen, bilirubin, pH, blood

- **DEXA scans (except Germany)**  
To be performed up to 2 weeks prior to the baseline visit (Visit 1) and again within 2 weeks of Visit 4. The DEXA scans will be performed according to the site's standard clinical procedures.
- **Quality of life questionnaires (QoL)**  
QOL questionnaires (MAF, SF-36® and EQ-5D™) will be administered after breakfast on the day when the subject is not fasted and completed in a quiet environment. To be administered at baseline and Visit 4.
- **Waist circumference, height and weight**  
Waist circumference, height and weight will be measured according to each site's normal clinical practice and the result recorded in the eCRF. The subject's BMI will be calculated and recorded in the eCRF.
- **ECG**  
ECG will be performed and reported locally, and the result recorded in the eCRF.
- **Physical examination**  
A full physical examination to assess the subject's general appearance and overall health will be carried out at screening and at the last visit in the study. Significant findings that are present **prior to** the start of study drug must be included in the relevant medical history/current medical status section of the eCRF and significant findings made **after** the start of study drug which meet the definition of an AE must be recorded in the eCRF. At the other visits, an abbreviated physical examination will be conducted if indicated by AEs, noting any changes from the screening assessment. Any abnormal findings will be recorded on the eCRF.

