### 13.3.5 Safety Variables

The safety variables are:

1. weight, BMI and waist circumference
2. routine haematology and clinical chemistry
3. physical examination
4. vital signs
5. urinalysis

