## Appendix 2 - Haematology and Clinical Chemistry Parameters

### **Clinical Chemistry**

Sodium, potassium, chloride, total CO2, creatinine, glucose, blood urea nitrogen (BUN), albumin, total calcium, total magnesium, inorganic phosphorus, alkaline phosphatase, ALT/GPT, AST/GOT, total bilirubin, direct bilirubin, lactate dehydrogenase (LDH), total protein, total creatine kinase (CK), uric acid, glucose, insulin, Hb1Ac, total cholesterol, high density lipoprotein (HDL) cholesterol, low density lipoprotein (LDL) cholesterol, triglycerides, hsCRP, osteocalcin, CTX, plasma renin

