#### 11.4.4. Urinalysis

The following urinalysis parameters will be collected: protein, specific gravity, ketones, urobilinogen, bilirubin, pH, blood.

For the continuous results (pH and specific gravity), change from baseline will be calculated at each visit (Week 4, Week 12, and Week 24) and summary statistics will be presented for both absolute values and change from baseline by treatment group, pre-baseline standard therapy and visit. In addition, boxplots of change from baseline in continuous urinalysis parameters over time will be produced along with a line connecting the mean change through time.

For all other urinalysis parameters, the frequency and percentage of subjects with results in each category, and shift table of baseline to worst on-treatment will be presented by treatment group, pre-baseline standard therapy and visit. Urinalysis variables will be listed by subject and time point. Values outside the normal ranges (provided with the laboratory report) will be flagged in the subject data listings.

Urinalysis results considered clinically significant by the investigator will be summarised.

A pregnancy test will also be carried out in female subjects of child bearing potential and the results will be listed.

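### Insulin/HOMA-IR, HbA1c, hsCRP, renin, CTX and osteocalcin have planned outputs only in the efficacy evaluable set, and urine glucose is missing from the SAP's urinalysis panel

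*SAP*

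**What the plan says.** **Protocol, safety role.** The clinical chemistry list in Appendix 2 includes "uric acid, glucose, insulin, Hb1Ac, total cholesterol" (HbA1c, as spelled there) and ends with "triglycerides, hsCRP, osteocalcin, CTX, plasma renin". Section 11.2 points to Appendix 2 for routine biochemistry. Section 13.3.5 names "routine haematology and clinical chemistry" among the safety variables. Section 13.1.1 promises that the tables and figures will be backed by complete subject listings.

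**Protocol, efficacy role.** Sections 7.3, 13.3.4 and 13.6.3 also make these analytes exploratory efficacy endpoints.

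**SAP.** Section 11.4.3 omits all six from routine biochemistry. Section 10.7.2 covers them as bone markers and laboratory assessments of special interest and adds HOMA-IR and total testosterone. It promises shift tables, a summary of clinically significant results and detailed listings, but names no analysis set. Appendix A does. In 14.1 the last of the tables is "Summary of clinically significant results for bone markers and laboratory assessments of special interest (Efficacy evaluable analysis set", and the summaries and shift tables carry the same set. The listing in 14.2 is "Bone markers and laboratory assessments of special interest (Efficacy evaluable analysis set". The boxplots in 14.3.1 use that set too.

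**Urinalysis.** Protocol 11.2 tests for "Protein, glucose, specific gravity, ketones, urobilinogen, bilirubin, pH, blood". SAP 11.4.4 states: "The following urinalysis parameters will be collected: protein, specific gravity, ketones, urobilinogen, bilirubin, pH, blood". Table 8 in SAP Appendix B also has no urine glucose row.

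**The concern.** Safety results are normally reported for everyone who was dosed, because reasons for exclusion from an efficacy set can be related to tolerability or treatment adherence. SAP 6.2 removes anyone without an evaluable week 24 17-OHP profile or with a major violation. A subject who withdraws after week 12, or who completes but has a major deviation, may have valid HbA1c, insulin and renin results that no planned table, listing or figure would show. That includes a result the investigator flagged as clinically significant.

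Renin has a direct safety use in this trial: Protocol 10.4 uses it to guide fludrocortisone adjustment, and Protocol 9.2 makes it an entry criterion. Insulin and HbA1c bear on the metabolic effects of glucocorticoid exposure. At stake is the completeness of the safety record. The primary comparison is not affected.

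**Working it through.** **1. The plan's own figure.** SAP section 5 gives 102 evaluable subjects, 120 randomised and 15% inevaluability.

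102 / (1 − 0.15) = 120, which reproduces the plan.

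**2. Subjects without planned output for these tests.**

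120 × 0.15 = 120 − 102 = 18.

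This assumes that all randomised subjects take at least one dose, so that the safety set has 120 members. Protocol Table 1 schedules these tests at baseline and at weeks 4, 12 and 24, so there are at most three scheduled on-treatment visits per subject, or 18 × 3 = 54 subject-visits. Early withdrawals contribute fewer.

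The true exclusion rate is not given. Over an assumed range of 5% to 25%, the count runs from 120 × 0.05 = 6 to 120 × 0.25 = 30.

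**3. Chance that something reportable is missed.** For a per-subject abnormality rate p, the chance of at least one affected subject among 18 is 1 − (1 − p)^18. The documents give no rate, so p is an assumption:

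| p | Chance of at least one in 18 |
|---|---|
| 2% | 30% |
| 5% | 60% |
| 10% | 85% |

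**4. Does another output cover these subjects?**

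| Data on an excluded subject | Planned set in SAP Appendix A |
|---|---|
| Insulin/HOMA-IR, HbA1c, hsCRP, renin, CTX, osteocalcin | Efficacy evaluable only |
| Blood glucose (Biochemistry 2) | Safety |
| Total, HDL and LDL cholesterol, triglycerides (Biochemistry 4) | Safety |
| Weight, BMI, waist, blood pressure (vital signs) | Safety |
| Adverse events | Safety |
| Signs and symptoms of adrenal insufficiency | Safety |

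The instruction in 14.1 to repeat efficacy outputs in the full analysis set applies to the outputs above it. It stands before the special-interest laboratory tables, and no such instruction follows them. In 14.2 the 17-OHP and A4 listing uses the full analysis set, so efficacy listings are not confined to the evaluable set as a rule.

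**5. Urine glucose.** The protocol names eight analytes and SAP 11.4.4 names seven. The missing one is glucose.

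**6. Is either point declared?** SAP section 12 records changes to shift tables and to dose-level splits. It mentions neither the analysis set for these analytes nor urine glucose.

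**The case against.** The strongest defence is that these analytes are exploratory efficacy endpoints and that the protocol makes the efficacy evaluable set primary for efficacy. The visit schedules also list them separately from routine biochemistry. SAP 10.7.2 follows that structure. This stands as far as it goes: the efficacy-set summaries are legitimate, and it is arguable whether section 12 needed an entry. But the protocol gives the analytes both roles, and the SAP itself plans safety-style outputs for them (shift tables and investigator-flagged results).

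A second defence is that clinically important results will surface elsewhere. Protocol 12.3.2 allows a clinically significant laboratory change to be recorded as an adverse event, and all adverse events are listed in the safety set. SAP 11.7.2 keeps fludrocortisone in the concomitant-medication outputs, so treatment changes prompted by renin would be visible. This narrows the gap without closing it, because recording as an adverse event is discretionary.

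Two stronger readings are tempting, and the documents support neither:

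- A reader might infer that the metabolic safety data of excluded subjects go wholly unreported. The comparison of analysis sets shows otherwise.
- A reader might infer that the excluded subjects are those most likely to be over- or under-replaced. SAP 10.2 also has deviation categories for eligibility, study procedure and local sampling, and a profile may be judged invalid because samples are missing. The allowance was raised from 7% to 15% because of protocol deviations (Protocol Appendix 10, Version 6.0), with no breakdown by type.

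On urine glucose, SAP 11.4.4 also says in general terms that urinalysis variables will be listed. A generous reading could cover glucose, but the enumerated panel and Table 8 do not.

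**Conclusion.** The point holds and is minor. For subjects outside the efficacy evaluable set, the SAP plans no table, listing or figure of insulin/HOMA-IR, HbA1c, hsCRP, plasma renin activity, CTX or osteocalcin, although the protocol classes the six measured tests as clinical chemistry and promises complete listings. The planned allowance puts this at about 18 of 120 subjects (6 to 30 over the assumed range). The figure is a planning allowance and not an observed count, and it assumes that everyone randomised is dosed. Whether abnormal results cluster in these subjects is unknown.

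Urine glucose is a separate, smaller inconsistency. It is collected for all subjects but named in no SAP panel, while blood glucose is fully reported for safety. Neither item touches the primary analysis, the sample size or the power.

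**What to change.** - In SAP 14.1 and 14.2, produce at least three outputs for these analytes in the safety analysis set: the listing, the shift tables from baseline to minimum and maximum on treatment, and the table of clinically significant results. State that set in 10.7.2.
- Keep the efficacy-set summaries for the exploratory comparison; they need not all be duplicated.
- Add urine glucose to SAP 11.4.4, Table 8 and the urinalysis tables and listing, or declare and explain its omission in section 12.

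The cost is a few lines of SAP text and a re-run of existing shells on another analysis set. No new data are needed.
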